15.0 Risks to Subjects*

15.1 No adverse events have been reported in relation to mindfulness-based intervention or tDCS. We have conducted several studies on tDCS and patients minimal side effects such as slight itching (present in 30% of people as reported by systematic reviews) or tingling on the scalp (present in 70% of people as reported in systematic reviews). Although we have not observed other side effects. Systematic reviews report the possibility of dizziness in 10% of people, nausea in 3% and headache in 11% of people. The Food and Drug Administration (FDA) has ruled that the aforementioned tDCS stimulator is a “non-significant risk” device, a requirement for Investigational Device Exceptions.

15.2 Patients may feel tired while completing questionnaires, but they can pause and resume at any time. Individual interviews and some items from questionnaires may allow emotions related to the experience of a major surgery to emerge. If psychological distress becomes obvious (verbatim or score on a questionnaire), the provider will be informed for follow-up and the patient will be encouraged to communicate with the clinic.

16.0 Potential Benefits to Subjects*

16.1 Based on previous studies, participants may use less opioids and experience less pain and anxiety. This reduction may allow for a better recovery and return to activities.

17.0 Data Management* and Confidentiality

17.1 The protocol will favor an intention-to-treat approach for the analysis of results.

PROTOCOL TITLE:

Data analysis will be performed with R (Vienna, Austria) version 4.1+. Baseline demographic information will be summarized using descriptive statistics. Continuous variables will be summarized with means and standard deviations. Categorical variables will be summarized with counts, proportions, and medians (interquartile range). The distribution of all variables will be examined before any analysis, using appropriate statistical tests like Shapiro's test for normality checking. If the assumption of normality is not met, equivalent non-parametric approaches or data transformation will be employed. The multiple testing problem will be accounted for using Bonferroni correction. All testing will be two-sided and 0.05 will be used as the familywise significance level. If needed, statistical analysis will also be conducted after controlling for baseline demographics and clinical characteristics (e.g., age, sex, and race).

For Aim 1, analgesic consumption measured on 3 consecutive days will be summarized into one number for each subject. Two-sample t-test (or non-parametric alternative) will be employed to determine the significance of the difference between the active and the sham tDCS+MBI groups. Multivariate linear regression will be further employed to account for potential confounding factors, including selected baseline demographics and clinical characteristics (e.g., age, sex, race, and body mass index). For Aim 2, we will conduct multivariable regression analysis to compare the change in clinical pain intensity (NRS, BPI, PHQ-4, PCS) from baseline to Day 3 in the postoperative phase after controlling for baseline and other confounding factors (e.g., age, race, sex, baseline NRS, consumption of pain medications). We will also determine whether the improvement conferred by active tDCS+MBI can be sustained by comparing the clinical pain intensity changes from baseline to 1 month between the active and the sham groups. We will also conduct sex-stratified analysis and explore whether there exists sex difference in these effects. For Aim 3, the QST dataset for endogenous pain modulation will be analyzed using multivariate linear regression for changes in each of the QST measures against potential confounding factors, and backward stepwise variable selection will then be performed to identify the parsimonious model structures. Spearman rank-order correlation will be used to quantify the association between changes in each of the QST measures and the changes in clinical pain intensity (NRS).

17.2. The PI, RA and research coordinator received the CITI training. Data will be de-identified and a code will be assigned to each participant.

17.3 Data entry will be validated at random.

17.4 Data (questionnaires, sociodemographic and clinical info) will have identifiers removed and banked for a minimum of 3 years per Federal regulations. Deidentified data will be available to research team: PI, co-I ([name] and [name]), RA, statistician ([name], CON). Data will be stored on a password-protected computer. The computer will be stored in a locked room. Any data collected online will be stored on an encrypted data server at the CON. Any downloaded data will be stored on a password protected computer. The RA supervised by the PI will be responsible for data receipt. [name] and [name] will assist with results interpretation.

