4.0 Study Endpoints*

- 4.1 Measures will be taken by a research assistant via a telephone interview using a Qualtrics® survey. Outcome measures will be taken at 4 time points: 1) baseline (before preoperative active/sham tDCS+MBI), 2) after 5 sessions of preoperative active/sham tDCS+MBI, 3) after surgery, and 4) 1 month after surgery (see table below)
- 4.2 Primary endpoint: Analgesic consumption. The dose of every opioid received within 5 days postoperatively will be transcribed and converted into standardized parenteral morphine equivalents using the Centers for Disease and Control Prevention Guidelines on opioids⁴². A total in milligrams will be calculated for each day and means will be obtained for all groups.
- 4.3 Secondary endpoints: pain severity (numeric rating scale 0-100), pain interference with activities (numeric rating scale 0-10), depression and anxiety (PHQ-4), pain catastrophizing (Pain Catastrophizing Scale), multimodal quantitative sensory testing (QST) including heat pain (e.g., threshold, tolerance), pressure pain threshold, punctate mechanical pain (e.g., suprathreshold ratings and temporal summation), and Conditioned Pain Modulation (CPM), acceptability and feasibility

Day/month	B	Preoperative phase	Postoperative phase
-----------	---	--------------------	---------------------

PROTOCOL TITLE:

		Day 1	Day 2	Day 3	Day 4	Day 5	Day 1	Day 2	Day 3	Month 1
Medical History Questionnaire	X									
Analgesic consumption (primary outcome)							X	X	X	X
Clinical Pain severity (secondary outcome)										
NRS	X					X			X	X
BPI	X					X			X	X
PHQ-4	X					X			X	X
PCS	X					X			X	X
Pain-related Cortical Response (secondary outcome)										
QST measures	X					X				
Acceptability and feasibility										
tDCS + MBI experience questionnaire						X				
Side effects questionnaire		X	X	X	X	X				

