6.0 Procedures Involved*

6.1 This study will use double-blind randomized sham-controlled design with an allocation ratio of 1:1 with repeated measures at 4 time points. Participants will be randomly assigned to one of 2 arms as follows: 1) preoperative active tDCS+MBI or 2) preoperative sham tDCS+MBI. Participants will be recruited at their preoperative visit (see letter of collaboration). A clinician (registered nurse or surgeon) or a research coordinator from the clinic will review the preoperative

PROTOCOL TITLE:

clinic schedule, conduct a pre-screening of potentially eligible participants, and introduce the study to potential participants at their preoperative visit by using a flyer. If the individual agrees to learn more, the PI or RA ([name]) will enter the room to discuss study, answer questions and sign the consent. If they agree to participate, after signing the consent, they will be invited to come to the brain stimulation laboratory (FSU innovation park) where a baseline assessment will be done before randomization by the RA or lab research coordinator ([name]). The tDCS device along with instructions will then be provided. The baseline visit will take approximately 2 hours. The preop procedures will be as follows with T = day of surgery:

T-7: Recruitment/Consent

T-6: Baseline lab measurements & tDCS fitting and training

T-5: AM & PM remote tDCS/MBI

T-4: AM & PM remote tDCS/MBI

T-3: AM remote tDCS/MBI + Post-intervention lab measurement & collect tDCS equipment

6.2 Measures:

Usual sociodemographic variables (i.e., age, sex, civil status, living conditions, education level, and employment status) will be assessed. Relevant medico-surgical information during hospitalization will be collected: type of surgery, postoperative complications, and current involvement in a rehabilitation program. The presence of chronic pain before surgery will also be documented.

Outcome measures will be taken at 4 time points: 1) baseline (before preoperative active/sham tDCS+MBI), 2) after 5 sessions of preoperative active/sham tDCS+MBI, 3) after surgery, and 4) 1 month after surgery. Table 1 gives an overview of all measures for the preoperative and postoperative phases.

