Study title:

Feasibility, Acceptability, and Preliminary Efficacy of Combined Transcranial Direct Current Stimulation and Mindfulness for Pain After Total Knee Arthroplasty

NCT Number: NCT05673720

Statistical analysis plan

October 10th, 2025

Data analysis was performed with R (Vienna, Austria) version 4.1+. Baseline demographic information was summarized using descriptive statistics. The distribution of all variables was examined before any analysis, using appropriate statistical tests like Shapiro's test for normality checking. If the assumption of normality was not met, equivalent non-parametric approaches were employed. Comparison between groups on changes from baseline in clinical variables as well as effect size (Cohen's d) calculation were conducted using Wilcoxon rank-sum test for score changes with non-normal distribution, and t -test for score changes with normal distribution. Considering the numerous repeated measures and the possibility of imbalances between measures, we conducted an analysis using a generalized mixed effects model to evaluate changes in all outcome measures for both preoperative and postoperative outcomes. Mixed effects models capture more information by offering more flexibility in the presence of missing data and treat time as a continuous variable. Mixed effects models are used for longitudinal observations and are capable of automatically adjusting for baseline differences, accounting for potential confounders (e.g., anxiety) when needed.

For the preoperative period, the analysis looked at differences between preoperative baseline and after 5 sessions with three fixed effects: Condition (Control vs. Treatment), Time (First vs. Last Session) and their interaction Condition*Time to test whether the treatment group showed different patterns of change compared to the control group over time in the preoperative period. For the postoperative period, the analysis looked at differences 1) between Day 1 Post-op vs. Day 5 Post-op, and 2) between Day 1 Post-op vs. 1-month post-op. Our model included three fixed effects: Condition (Control vs. Treatment), Time (Day 1 vs. Day 5 or Day 1 vs. 1-month post-op), and their interaction (Condition*Time) to test whether the treatment group showed different patterns of change compared to the control group over time in the postoperative period.

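### The test that decides Hypothesis 1 is unadjusted, and baseline pain and catastrophizing scores, scheduled for everyone before randomization, are not named as covariates for opioid use

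*Protocol*

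**What the plan says.** Protocol section 4.2 gives the label: "Primary endpoint: Analgesic consumption". For Aim 1, section 17.1 says that "analgesic consumption measured on 3 consecutive days will be summarized into one number for each subject", and then: "Two-sample t-test (or non-parametric alternative) will be employed to determine the significance of the difference between the active and the sham tDCS+MBI groups". The next sentence adds a regression for potential confounders, "including selected baseline demographics and clinical characteristics (e.g., age, sex, race, and body mass index"). The list is open, and it contains no pain or catastrophizing score.

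The baseline scores exist. Section 4.1 says: "Outcome measures will be taken at 4 time points: 1) baseline (before preoperative active/sham tDCS+MBI"). The schedule table marks NRS, BPI, PHQ-4 and PCS at baseline. Section 4.3 lists "pain catastrophizing (Pain Catastrophizing Scale") among the secondary endpoints. Section 6.1 says that "a baseline assessment will be done before randomization", so these scores are valid adjustment covariates. For Aim 2, section 17.1 does name baseline NRS as a covariate.

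The SAP tests changes from baseline with a t-test or Wilcoxon test, and also fits a mixed model to all outcome measures. For the postoperative period it says: "Our model included three fixed effects: Condition (Control vs. Treatment"), then time and the interaction. It allows for confounders where needed, with anxiety as the example. It does not mention opioid use separately, or say how its models relate to the protocol's two-sample test.

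**The concern.** Pain and catastrophizing before surgery are plausible predictors of opioid use after it. The protocol itself treats pain and analgesic use as linked, since its Aim 2 model controls for consumption of pain medication. In a trial of 20 per arm, a modest prognostic covariate can be worth several patients, and these two need no new measurement.

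The second issue is discretion. Adjustment is left to selected covariates in the Aim 1 regression, and to an if-needed or when-needed basis elsewhere in section 17.1 and in the SAP. The SAP also drops the Bonferroni correction and reads p < 0.10 as suggestive. A covariate set that is not fixed in advance then makes a favourable adjusted result harder to interpret.

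**Working it through.** **Inputs from the documents.** N = 40 completers (section 12.1); allocation 1:1 (section 6.1), so 20 per arm; two-sided testing at 0.05 (section 17.1; any Bonferroni division is ignored here). The plan states no effect size, SD, power or covariate-outcome correlation, so it has no figure to reproduce.

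**Assumptions.** R² is the share of opioid-use variance explained jointly by one baseline NRS item and the PCS total. It is varied from 0 to 0.30. A standardized difference d = 0.8 is used for illustration only.

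**Variance ratio, adjusted model against t-test.** With p covariates the ratio is (1 − R²) × (N − 3)/(N − 3 − p). For N = 40 and p = 2 this is (1 − R²) × 37/35. The equivalent unadjusted N is 40 divided by the ratio.

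| Assumed R² | Variance ratio | Equivalent unadjusted N |
|---|---|---|
| 0 | 1.057 | 37.8 |
| 0.05 | 1.004 | 39.8 |
| 0.10 | 0.951 | 42.0 |
| 0.20 | 0.846 | 47.3 |
| 0.25 | 0.793 | 50.4 |
| 0.30 | 0.740 | 54.1 |

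Break-even: R² = 1 − 35/37 = 0.054, a multiple correlation of √0.054 = 0.23.

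**Power at d = 0.8** (noncentral t, 38 df unadjusted and 36 df adjusted). The t-test has 69.3%. The adjusted model has 66.8% at R² = 0, 69.0% at 0.05, 71.4% at 0.10, 76.3% at 0.20 and 81.6% at 0.30. A simulation of 10,000 runs per setting agrees (t-test against adjusted): 69.8% and 67.5% at R² = 0; 68.8% and 70.4% at 0.10; 68.6% and 76.1% at 0.20; 70.1% and 82.1% at 0.30.

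**Length of the covariate list.** Adding NRS and PCS to the protocol's four examples gives p = 6 at one degree of freedom each, and a ratio of (1 − R²) × 37/31: 1.19 at R² = 0, 1.07 at 0.10, 0.96 at 0.20 and 0.84 at 0.30. Break-even rises to 1 − 31/37 = 0.16. The list needs to be short.

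**Whether the SAP model supplies the adjustment.** The SAP says that mixed models can adjust automatically for baseline differences. The schedule marks analgesic consumption only on postoperative Days 1 to 3 and at Month 1. There is no preoperative value from which to form a change. Both time points in each of the SAP's postoperative comparisons (Day 1 with Day 5, Day 1 with 1 month) come after treatment. With only the three listed fixed effects, no pre-randomization information on opioid use enters.

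**The case against.** Several objections have force.

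- *Adjustment is planned.* A reader might infer that Aim 1 has no adjusted analysis, or that the SAP's models exclude covariates altogether. Neither is supported. Section 17.1 adds a regression whose open list could include baseline pain, and the SAP allows confounders when needed. What remains is that this adjustment is supplementary or optional, and that its covariates are not fixed.
- *The gain is not established.* A reader might infer that the unadjusted test certainly gives precision away. The documents give no R². Below about 5% the two covariates slightly reduce precision, and at 10% the gain is small. This stands in full.
- *The unadjusted test is valid.* Under randomization, chance imbalance is already reflected in its standard error. The documents give no ground for calling the test biased. The issue is precision and pre-specification.
- *The ratios compare with the t-test only.* If normality fails, the plan moves to a non-parametric test, and no comparison with that branch was made.
- *The stakes are limited.* Section 1.0 gives feasibility and acceptability as the primary objective, and the SAP describes a pilot as generating hypotheses. This lowers the weight of the point. It does not explain why scores already scheduled are left out of the comparison for the endpoint that section 4.2 labels primary.
- *It may be too late.* The SAP is dated October 10th, 2025 and written in the past tense, so a covariate set chosen now may be post hoc. The fix has to allow for that.

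**Conclusion.** The point holds as a recommended improvement. Hypothesis 1 is decided by an unadjusted test, and two relevant scores scheduled for everyone before randomization are named neither for Aim 1 nor among the SAP's fixed effects. A short, fixed adjusted model is the better main analysis because its downside is small and bounded: 6% in variance, or 69.3 − 66.8 = 2.5 points of power at d = 0.8, if the scores explain nothing. At an assumed R² of 0.10 to 0.25 the variance falls to between 0.95 and 0.79 of the t-test's, equivalent to about 42 to 50 unadjusted patients in place of 40. That rests on the assumed R², on N = 40 with two covariates, and on a scale on which a linear model is reasonable.

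**What to change.** Make the main Hypothesis 1 comparison a linear model of each participant's opioid total on arm, one named baseline NRS item and the baseline PCS total. Section 6.2 lists four NRS items, three of them on movement, so one must be chosen; the 7-day average on movement is a reasonable candidate. Fix one way of handling skew that copes with zero totals, for example log(x + 1) or a permutation p-value, rather than leaving it to a normality test. Keep the two-sample test as a sensitivity analysis on the same total.

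If outcome data have already been seen, leave the planned test in place, report the adjusted model beside it, label it post hoc, and pre-specify it for any follow-on trial.

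The cost is a change of SAP wording and two degrees of freedom, with a slight loss of precision if the covariates are not prognostic. No new data collection is needed.

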2.0 Objectives*

2.1 The goal of this project is to assess the preliminary feasibility, acceptability, and efficacy of self-administered preoperative tDCS+MBI in older adults (50+) undergoing TKR. The central hypothesis is that combined preoperative tDCS+MBI will decrease postoperative analgesic consumption, postoperative clinical pain severity, as well as preoperative pain-related cortical response. We will accomplish three aims using a randomized controlled trial.

2.2 *Hypotheses:*

To determine the effects of 5, 20-minute preoperative self-administered tDCS sessions combined with brief MBI on analgesic medication consumption following TKR

Hypothesis 1: participants receiving preoperative active tDCS+MBI will show reduced postoperative analgesic consumption.

To determine the effects of 5, 20-minute preoperative self-administered tDCS sessions combined with brief MBI on postoperative pain severity following TKR

Hypothesis 2: participants receiving preoperative active tDCS+MBI will show reduced postoperative pain intensity and pain interference with physical and emotional function 5 days and 1 month after TKR.

To explore the effects of 5, 20-minute preoperative self-administered tDCS sessions combined with brief MBI on preoperative endogenous pain modulation

PROTOCOL TITLE:

Hypothesis 3: participants receiving preoperative active tDCS+MBI will show improved preoperative endogenous pain modulation.

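### The Aim 2 pain regression lists pain-medication use as a confounder without a time point; the only scheduled measure is the post-randomisation primary endpoint, and adjusting for it biases the pain effect in an unpredictable direction.

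*Protocol*

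**What the plan says.** Protocol section 17.1 analyses Aim 2 by multivariable regression. The outcome is the change in the pain and related scores "from baseline to Day 3 in the postoperative phase after controlling for baseline and other confounding factors". The bracketed examples of those factors are age, race and sex, followed by "baseline NRS, consumption of pain medications". NRS carries a baseline label; the medication item carries no time point.

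Section 4.2 states "Primary endpoint: Analgesic consumption" and defines it: "The dose of every opioid received within 5 days postoperatively will be transcribed". The schedule table in section 4.0 marks this measure at postoperative Days 1, 2 and 3 and at Month 1. It has no mark at baseline or in the preoperative phase. Section 6.1 says that "a baseline assessment will be done before randomization", and the sessions and surgery come later. Hypothesis 1 in section 2.2 reads "participants receiving preoperative active tDCS+MBI will show reduced postoperative analgesic consumption".

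The only baseline instrument that might hold medication use is the "Medical History Questionnaire", whose content is not described.

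The SAP, dated October 2025 and written in the past tense, describes a different analysis: group comparisons of change from baseline, and mixed models with condition, time and their interaction as fixed effects. It names no medication covariate. It does say that such models can account for confounders where necessary, gives anxiety as its one example, and does not restrict these to values taken before randomisation.

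**The concern.** In a randomised comparison, baseline covariates are balanced in expectation, and adjusting for them gains precision without changing what is estimated. A variable measured after randomisation that treatment may alter is different. Opioid use in the days after surgery may carry part of any treatment effect on pain. It also responds to pain and shares causes with it. Conditioning on it compares patients who reached the same opioid use by different routes in the two arms, and this is no longer the comparison that randomisation protects.

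Hypothesis 2 concerns the effect of the intervention on postoperative pain as a whole. A coefficient adjusted for postoperative consumption answers another question. It also sits badly with the intention-to-treat approach that section 17.1 favours. The SAP treats p below 0.10 as a signal worth further study, so a distorted pilot estimate could influence whether a later trial is run.

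**Working it through.** **Placing the covariate in time.** Baseline assessment comes first, then randomisation, then five preoperative sessions, surgery, and postoperative Days 1 to 3 and Month 1 (sections 6.1 and 4.0). All four scheduled analgesic marks fall after randomisation. By Hypothesis 1, treatment is expected to shift this variable. If it is the one meant in Aim 2, it is an outcome and not a baseline confounder.

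**Size of the distortion.** The documents give no effect size, SD, correlation or sample-size derivation, so there is no stated figure to reproduce. The three inputs below are assumptions, in SD units, with reductions negative:

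- tau: total effect of treatment on pain
- a: effect of treatment on consumption
- rho: within-arm slope of pain on consumption

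Write pain as Y = tau·T + e_Y and consumption as M = a·T + e_M, where T is arm. Least squares of Y on T and M gives M the coefficient rho. Since tau is the sum of the arm coefficient and rho·a, the arm coefficient is

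adjusted effect = tau - rho·a.

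The same holds with baseline covariates in the model if all three quantities are read as conditional on them.

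| tau | a | rho | tau - rho·a | Change in estimated benefit |
|---|---|---|---|---|
| -0.50 | -0.50 | +0.5 | -0.50 + 0.25 = -0.25 | 50% removed |
| -0.50 | -0.50 | +0.3 | -0.50 + 0.15 = -0.35 | 30% removed |
| -0.50 | -0.50 | 0 | -0.50 | none |
| -0.50 | -0.50 | -0.3 | -0.50 - 0.15 = -0.65 | 30% exaggerated |
| -0.50 | 0 | any | -0.50 | none |
| 0 | -0.50 | +0.3 | +0.15 | spurious harm |
| 0 | -0.50 | -0.3 | -0.15 | spurious benefit |

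Simulation with 200,000 subjects per scenario agreed with the formula to about 0.01 SD in the scenarios with tau of -0.5 or -0.8. The two null rows come from the formula alone. With tau = -0.50, the widest assumptions run from -0.74 (a = -0.8, rho = -0.3; 48% exaggerated) to +0.06 (a = -0.8, rho = +0.7; more than all of the effect removed).

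**Sign of rho.** If patients in more pain take more opioid, the slope is pushed positive. If opioid relieves pain, it is pushed negative. Both mechanisms act in the same patients, and nothing in the documents says which dominates at Day 3.

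**The SAP's example.** Anxiety is measured by the PHQ-4, scheduled at baseline, after the sessions, at postoperative Day 3 and at Month 1. It is also a secondary endpoint (section 4.3). An anxiety covariate taken after baseline would raise the same difficulty.

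**The case against.** The strongest reply is that the protocol may have meant preoperative use. The item is one example in a list and has no time point. It directly follows a baseline-labelled variable, and that label could be read as covering both. Elsewhere section 17.1 speaks of baseline characteristics, both in its general rule and in Aim 1. The term is also broader than the opioid dose that defines the primary endpoint. Medication information may exist before surgery, through the medical history form or through the eligibility check on current use of certain drug classes in section 10.0. This reading is possible and cannot be excluded. But no preoperative analgesic measure is scheduled or described, and the text leaves the analyst free to use the one that is.

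The second reply is that the SAP has moved on: its fixed effects contain no medication term. That stands, and it places the flaw in the protocol's Aim 2 model. The SAP does not, however, say that the Aim 2 regression is replaced, and its allowance for confounders has no time limit.

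A reader might infer that the adjustment must remove part of the treatment effect, or pull it towards zero whenever both hypotheses are true. The documents do not support this. Attenuation also needs a positive within-arm slope. With both effects at -0.50 SD, a slope of -0.3 exaggerates the benefit. A reader might also infer that the reported results were adjusted in this way; nothing in the SAP shows that.

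**Conclusion.** The point holds in a limited form. Protocol section 17.1 admits a covariate whose only scheduled measurement is a post-randomisation outcome that the trial expects treatment to change. If that measurement is used, the arm coefficient does not estimate the total effect on pain. Under an assumed 0.50 SD effect on both variables, the estimated benefit runs from 0.25 to 0.65 SD as the slope goes from +0.5 to -0.3. It is unchanged if the slope is zero or if treatment does not affect consumption. The direction cannot be predicted, so a reader could not allow for it.

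The sizes rest wholly on assumed inputs; the timing argument rests on the documents. If preoperative use was intended, the defect shrinks to a missing time point. The matter concerns secondary endpoints in a pilot of 40 completers. It should be corrected, but it does not undermine the trial.

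**What to change.** 1. Delete the medication item from the Aim 2 covariates in section 17.1. Alternatively, name preoperative analgesic use, provided it was recorded before randomisation.
2. State in both the protocol and the SAP that covariates are limited to values obtained before randomisation. For the SAP's example, this means baseline anxiety.
3. Label any model adjusted for postoperative consumption as exploratory, and do not present its arm coefficient as the effect on pain.
4. Have the sponsor confirm whether the SAP's models replace the Aim 2 regression, and list the covariates that were used in each reported model.

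Deletion and the wording changes need a few lines and no new data. Substituting preoperative use costs nothing only if it was already collected; otherwise that option is not available without new data.

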11.0 Vulnerable Populations*

11.1 N/A

12.0 Local Number of Subjects

12.1 N=40 (completers)

13.0 Recruitment Methods

An experienced research assistant (RA) and/or the PI will be responsible of participants' recruitment and informed consent procedures.

The research coordinator ([name]) will review the preoperative clinic schedule. The individual will conduct a pre-screening of potentially eligible participants (see attached HIPAA waiver). A clinician (Registered nurse, [name]) will introduce the study to potential participants at their preoperative visit by using a flyer. If the individual agrees to learn more, the PI or RA will enter the room to discuss study, answer questions, sign the consent and schedule the visit to the lab. Before any in-person interaction, COVID-19 screening will be conducted.

PROTOCOL TITLE:

The PI and RA are fully vaccinated, they will use the CDC self-checker tool and wear a mask at all times, as well as respect the clinic's current policies. Patients usually receive a COVID screening before starting their visit at the clinic and the clinician will inform them about FSU COVID-19 precautions and distribute the FSU Information sheet.

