The significance levels (Type-I error probability) for testing the difference between treatment groups over time was 5% and a p-value less than 0.05 was considered statistically significant. However, this level might seem arbitrary in pilot studies and we considered that in this preliminary study, $p < 0.10$ is suggestive (i.e. a trend) of a significant effect that warrants further study. We did not use any Bonferroni corrections for these pair-wise comparisons since a pilot study is usually designed for hypothesis generation instead of hypothesis testing.

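### The protocol explores a sex difference in the Aim 2 effects by sex-stratified analysis but specifies no arm-by-sex comparison, and the SAP omits the sex analysis without explanation

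*Protocol*

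**What the plan says.** The Aim 2 paragraph of Protocol section 17.1 plans a multivariable regression to "compare the change in clinical pain intensity (NRS, BPI, PHQ-4, PCS) from baseline to Day 3", with a second comparison at 1 month. It then adds: "We will also conduct sex-stratified analysis and explore whether there exists sex difference in these effects". Stratification is the only technique named for the sex question. Elsewhere in section 17.1 sex appears only as an adjustment covariate.

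The trial is a "double-blind randomized sham-controlled design with an allocation ratio of 1:1" (section 6.1), and section 12.1 gives the size as "N=40 (completers". Neither document gives an expected sex split or says that randomisation is stratified by sex.

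On error control, Protocol section 17.1 says "The multiple testing problem will be accounted for using Bonferroni correction" and "All testing will be two-sided and 0.05 will be used as the familywise significance level", without giving the number of tests in the family. The SAP's closing paragraph says "We did not use any Bonferroni corrections for these pair-wise comparisons" and that p < 0.10 "is suggestive (i.e. a trend) of a significant effect that warrants further study".

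The SAP has no sex-stratified analysis and no sex term. Its only interaction is condition by time. Where the protocol had the Aim 2 regression, the SAP describes change-score tests and mixed models.

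**The concern.** The protocol wants to know whether the treatment effect differs between men and women. The quantity for that is the difference between the two sex-specific effects, with its uncertainty. Two separate analyses do not give it unless they are formally compared. With small strata, one p-value can easily fall below the threshold and the other above it when the true effects are identical. A reader of such a result may see a sex difference that is not there, and will not see how imprecise the comparison is.

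The stakes are modest but real. The SAP presents the pilot as hypothesis-generating, and a chance sex difference is the kind of result that can be carried into the next trial's design. A second issue is traceability. A planned analysis is absent from the SAP, so a reader cannot tell whether it was dropped, or was done and not described.

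**Working it through.** The documents give no effect size, SD or power figure, so there is no planned figure to reproduce.

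**Inputs from the documents.** 40 completers (Protocol 12.1) at 1:1 (6.1) gives 20 per arm. Tests are two-sided at 0.05 (17.1). Aim 2 has four instruments and two time contrasts (17.1).

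**Assumptions.** An even sex split, so 40/2/2 = 10 per arm per sex, with 14/6 per arm as a variation. The same true standardised effect d in both sexes, from 0 to 0.8. An unadjusted two-sample t-test on change within each sex. For Bonferroni, a family of 4 outcomes × 2 sexes = 8, so 0.05/8 = 0.00625.

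**Step 1: power p within one sex.** Noncentral t with 18 df and noncentrality d × √(10/2) = 2.236d.

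**Step 2: chance that exactly one sex is significant.** The strata are independent, so this is p_F(1 − p_M) + p_M(1 − p_F), which is 2p(1 − p) for an even split. At d = 0.8: 2 × 0.395 × 0.605 = 0.478.

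| Common effect d | Power per sex at 0.05 | Exactly one significant at 0.05 | Same, 14/6 split | Same, at 0.05/8 (even split) |
|---|---|---|---|---|
| 0 | 5% | 9.5% | 9.5% | 1.2% |
| 0.3 | 9.7% | 18% | 18% | 3% |
| 0.5 | 18.5% | 30% | 31% | 8% |
| 0.8 | 39.5% | 48% | 52% | 23% |

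For larger effects the unadjusted figure at an even split levels off and then falls: 49% at d = 1.0 and 40% at d = 1.2. If the SAP's p < 0.10 were applied within sex, it would be 18%, 41% and 50% at d = 0, 0.5 and 0.8. Counting both time contrasts gives a family of 16 (0.05/16 = 0.0031), with about 0.6%, 2%, 5% and 16% at d = 0, 0.3, 0.5 and 0.8.

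**Step 3: four outcomes together.** In a simulation of 20,000 trials with between-outcome correlation of 0.5 or 0, at least one of four outcomes was discordant at unadjusted 0.05 in 28% to 33% of trials at d = 0 and in 66% to 76% at d = 0.5.

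**Step 4: the direct comparison.** The arm effect within one sex has SE √(2/10) SD. The difference between two independent such effects has SE √(2/10 + 2/10) = √0.4 = 0.63 SD. The overall arm effect has SE √(2/20) = 0.32 SD, half as large. With 36 df the critical t is 2.03, so the 95% CI for the sex difference is about ±2.03 × 0.632 = ±1.28 SD. A test of this contrast at 0.05 gives a false sex difference 5% of the time per outcome, whatever the common effect. Its power is 12% for a true sex difference of 0.5 SD and 34% for 1.0 SD. It reaches 80% only at about 1.83 SD.

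**The case against.** The strongest objection is that the protocol's sentence has two parts, and the second leaves the method of comparison open. An interaction term in the Aim 2 regression, where sex is already a covariate, would fit it. A reader might infer that the investigators chose stratification in place of an interaction, or that they intend to read a sex difference from one significant and one non-significant p-value. The documents support neither inference. They are silent, and the supportable point is that no between-sex comparison is specified.

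The larger percentages can also be over-read. No document pairs a sex-stratified analysis with unadjusted testing: the protocol plans the sex analysis and applies Bonferroni, while the SAP drops Bonferroni and has no sex analysis. Ten per cell is an assumption and not a feature of the plan. The t-test is a simplification of a covariate-adjusted regression.

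Finally, the analysis is exploratory, in a pilot, and the interaction has too little power to settle the question. All of this stands, and it limits the size and tone of the point. It does not remove the gap: neither document names an estimate of the quantity the protocol says it will explore, and the SAP does not say what became of the analysis.

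**Conclusion.** The point holds as an under-specification and reporting risk. It is minor and touches no primary or main secondary comparison. A reader might infer that this plan will often produce a spurious sex difference. The documents do not support that, because the rate depends on three things they do not settle: the true effect, the multiplicity rule applied, and whether the sexes are compared by significance. If they are, the chance of a discordant pair per outcome runs from 9.5% (no effect) to 48% (0.8 SD in both sexes) at unadjusted 0.05, and from about 1% to 23% at 0.05/8. These ranges rest on the even split and equal effects assumed above. A more uneven split changes the unadjusted figures little but leaves as few as 6 per arm in the smaller sex at 14/6.

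**What to change.** State in the SAP whether the sex analysis was kept or dropped, with the reason if dropped.

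If it was kept:
- Fit one model per outcome on all participants, adding sex and arm-by-sex to the protocol's Aim 2 regression. In the SAP's mixed model, add sex with its lower-order interactions, and take arm-by-sex-by-time as the term of interest.
- Report the interaction estimate with its 95% CI, labelled exploratory.
- Give sex-specific estimates with CIs as description, and draw no sex difference from comparing within-sex p-values.
- Report the number of participants per arm and sex.

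The cost is a few model terms and a short paragraph in the SAP, with no new data. The downside is imprecision: with an SE of about 0.63 SD, the interaction can only be reported as an estimate with its uncertainty. A wide interval must not be read as evidence that the sexes respond alike.
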